5.10. Concomitant Therapy and Procedures

The use of any concomitant medication, prescription or over the counter, taken within 30 days prior to signing consent, is to be recorded on the source document and corresponding CRF along with the reason the medication was taken.

Concurrent enrollment (within 90 days of enrollment) in another investigational drug or medical device clinical trial is not permitted.

5.11. Prohibited Concurrent Therapies and Procedures

Prohibited medications, treatments, and procedures during the clinical trial are outlined in the Exclusion Criteria (Section 3.5.2).

6. CLINICAL TRIAL PROCEDURES

Clinical trial assessments and evaluations should be performed by the investigator and/or qualified site staff according to Schedule of Events and Assessments (Table 1). Refer to the Clinical Trial Activities Schedule (Section 7).

6.1. Informed Consent

Informed consent forms must be approved for use by the reviewing Institutional Review Board (IRB)/Research Ethics Board (REB)/Independent Ethics Committee (IEC). Informed consent must be obtained for all subjects participating in the clinical trial prior to performing any procedures. The informed consent process must be adequately documented in the source records.

6.2. Eligibility Review

The investigator or qualified site staff will confirm that all inclusion and exclusion criteria have been met.

6.3. Demographics, Medical History, and Social History

Demographic information to be captured include subject initials (where locally permitted), date of birth (alternatively year of birth, if full date of birth is not allowed to be collected for legal reasons), age, sex, race, and ethnicity will be obtained from the subject and recorded in the CRF.

Medical and social history will be recorded in the CRF. Current underlying conditions, including conditions diagnosed within the last 30 days of consent, which may have resolved before screening, must be recorded.

6.4. Concomitant Medications

Concomitant medications used 30 days prior to consent to treat any medical conditions will be recorded in the CRF. Any changes in dosage or new medications added must be recorded in the subject CRF. The Sponsor and investigator or qualified site staff will review and evaluate concomitant medication usage on an ongoing basis.

6.5. Adverse Events

Any serious, unexpected adverse events (AE) believed to be due to the intervention rather than the natural disease process will prompt a filing of an adverse event form with the local IRB office and the FDA.

AEs will be collected from the time the subject signs the informed consent form through 30 days after the last dose of IP. AEs must be recorded in the CRF. The Sponsor and investigator or qualified site staff will review and evaluate AEs on an ongoing basis. See Section 8 for further detail on AE reporting.

6.6. Urine pregnancy testing

For women of childbearing potential (WOCBP), a urine pregnancy test will be collected at the Screening Visit B (Visit 2), and prior to each injection of ADX-2191, through Visit 8 / Week 10. Results must be available and confirmed to be negative before the subject may be enrolled in the clinical trial. IP must be discontinued for any subject with a positive pregnancy test result.

6.7. Ophthalmic Examinations

6.7.1. Best-Corrected Visual Acuity

BCVA will be collected at Screening Visit A (V1), Screening Visit B (V2), and Visits V3, V5, V7, V9, and V10. The BCVA will be measured using ETDRS chart by masked technicians at a standard photopic light level of at least 85 cd/m². Both eyes will be examined at all time points.

6.7.2. Low Luminance Visual Acuity

Low-luminance visual acuity (LLVA) will be collected at Screening Visit A (V1), Screening Visit B (V2), and Visits V3, V5, V7, V9, and V10. LLVA will be assessed using a 2.0 log unit neutral density filter while reading a normally illuminated ETDRS (Early Treatment Diabetic Retinopathy) chart. If <20 letters are read at 4 meters, testing should be repeated at 1 meter. Both eyes will be examined at all time points.

6.7.3. Macular Integrity Assessment (MAIA) Microperimetry

Central retinal sensitivity will be assessed using MAIA microperimetry using a standard 10-2 test grid with a 4-2 bracketing threshold strategy and Goldman size III stimulus of various intensities presented on a mesopic background (4 apostilbs). MAIA will be collected at Visits V1, V2, V3, V5, V7, V9, and V10. Only the study eye will be evaluated.

6.7.4. Full Field Electroretinography

A standard full-field electroretinogram (ERG) will be performed. Change in dark-adapted flash (0.01 cd•s•m⁻²) b-wave amplitudes will be analyzed. Testing will be performed using a standard

International Society for Clinical Electrophysiology of Vision (ISCEV) protocol. Both eyes will be evaluated. ERG will be collected at Visits V1 and V9.

6.7.5. Dark-Adapted Chromatic (DAC) Perimetry

Change in dark-adapted retinal sensitivity (dB) to the cyan (blue) and red stimuli on the Medmont Dark-Adapted Chromatic (DAC) perimeter will be assessed. The test eye will be patched for 45 minutes to allow for dark adaptation. At each test point the stimulus will be presented with either a cyan (505 nm, 75 dB maximum dynamic range) or a red (620 nm, 50 dB maximum dynamic range) color. 103 points (144 ° horizontally and 72 ° vertically) will be tested using a 1.72° stimulus (equivalent to the Goldman size V) will be presented for 200ms, with a 400ms response time, and fixed interval between stimuli at 1.1 seconds. Retinal sensitivities will be determined using a four-down, two-up staircase threshold strategy. The maximum photopic luminance for the cyan stimuli will be no more than 12.58 cd/m² with a test range of 0 to 75 dB attenuation. For the red stimuli, the maximum luminance will be no more than 4.64 cd/m² with a range of 0 to 50 dB. Appropriate lenses should be used for correction of refractive error and age-related accommodation loss. Patient controlled pauses are encouraged as often as needed to reduce to prevent fatigue. Exams with >20% false positives will be excluded. Only the study eye will be evaluated. DAC Perimetry will be collected at Visits V1, V2, V3, V5, V7, V9, and V10. Only the study eye will be evaluated.

6.7.6. Macular Spectral-Domain Optical Coherence Tomography (SD-OCT)

Macular SD-OCT imaging will be done; the Heidelberg Spectralis is preferred. Both eyes will be imaged at Visits V1 and V10. The macular volume scan should be obtained using the preset “Posterior Pole settings: **Scan Extent:** Volume Scan (30° x 25°); **Scan Sections/B-scans:** 61 sections (with a 120 µm spacing); **Resolution:** High Speed with an ART mean of at least 9 frames. SD-OCT will be collected at Visits V1, V5, V7, V9, and V10. Both eyes will be evaluated at visits V1, V9, V10 and only the study eye will be evaluated at V5 and V7.

6.7.7. Full Ophthalmic Clinical Examination

Routine full ophthalmic, dilated exams, including intraocular pressure measurement, slit lamp examination, and dilated funduscopy will be performed on Screening Visit A (V1) and Visits V3, V5, V7, V9, V10. Both eyes will be examined at all time points. The full ophthalmic exam will also serve as the corneal safety assessment on days when a full ophthalmic exam is done prior to an intravitreal injection.

6.7.8. Color and Autofluorescence Fundus Photographs

All subjects will undergo pre-operative color and autofluorescence photographs. Both eyes will be imaged at Visits V1, V9, and V10. The Optos UWF or Zeiss CLARUS are preferred;

appropriate dilation prior to acquiring imaging is recommended. A single ultra-widefield image with minimal artifacts and good exposure is required. High resolution TIF, BMP, JPEG, PNG, or DICOM file formats are accepted. Photographs will be collected at Visits V1, V9, and V10.

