2.2. Clinical Trial Endpoints

2.2.1. Primary Endpoints

The primary endpoint is safety and tolerability of ADX-2191.

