9.2.5. Primary Endpoint Analyses

Safety endpoints will be summarized descriptively. Safety endpoints include:

- Slit-lamp evaluation
- Dilated ophthalmoscopy
- Adverse event (AE) query (reported, elicited, and observed)

Adverse events will be summarized descriptively. Frequencies and percentages will be provided per treatment group of subjects with treatment-emergent adverse events (TEAEs), serious TEAEs, and TEAEs causing premature discontinuation. An adverse event is treatment-emergent if it occurs after the first dose of investigational treatment. Furthermore, frequencies will be given of subjects with TEAEs by system organ class, by system organ class and preferred term, by system organ class, preferred term and maximal severity, by system organ class, preferred

term and strongest relationship, and by system organ class, preferred term, maximal severity, and strongest relationship.

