9.2.6. Secondary Endpoint Analyses

Secondary endpoints will be analyzed to evaluate for change from Screening Visit B (Visit 2) to the level at Week 16 (Visit 10). Change from Screening level will be the dependent variable. The secondary endpoints include letters of BCVA or LLVA, improvement in visual field area and microperimetry, and increase in dark-adapted flash b-wave amplitudes.

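### Fundus photographs and autofluorescence feed no stated analysis, and ERG and OCT are outside the listed safety endpoints with no computable change in Section 9.2.6, so retinal loss on these tests has no systematic route into the primary safety result

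*Combined protocol and SAP*

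**What the plan says.** Section 2.2.1 makes safety primary: "The primary endpoint is safety and tolerability of ADX-2191". Section 9.2.5 gives its analysis: "Safety endpoints will be summarized descriptively. Safety endpoints include" slit-lamp evaluation, "Dilated ophthalmoscopy" and "Adverse event (AE) query (reported, elicited, and observed"). Photographs, autofluorescence, OCT and ERG are not on that list.

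Section 6.7.8 and Table 1 schedule color and autofluorescence photographs of both eyes: "Photographs will be collected at Visits V1, V9, and V10". Section 6.7.8 names preferred devices and accepted file formats, but no reading or grading rule. Neither the synopsis, Section 2.2.2, Section 9.2.5 nor Section 9.2.6 mentions these images.

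Section 6.7.4 schedules the ERG in both eyes: "ERG will be collected at Visits V1 and V9". Section 6.7.6 schedules OCT at V1, V5, V7, V9 and V10. Section 2.2.2 lists both among the secondary endpoints and words both as a change.

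Section 9.2.6 sets the secondary analysis as change from V2 to V10. It lists visual acuity letters, "improvement in visual field area and microperimetry, and increase in dark-adapted flash b-wave amplitudes". OCT is not named there.

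**The concern.** The primary question is safety, in eyes with a progressive photoreceptor degeneration that receive three or six intravitreal injections. The tests that measure retinal function and structure objectively are already being done: b-wave amplitude, central subfield thickness, ellipsoid zone extent and autofluorescence. Yet the primary result, as specified, contains no summary of any of them. Their secondary analysis would not reliably show a loss either. The ERG is described in the direction of benefit, OCT has no stated analysis, and the stated visits do not fit either test.

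With about eight subjects and no control arm, by-subject tables of these measures are among the most informative safety displays the trial can offer. Without them, the primary report could be silent on an asymptomatic fall in b-wave amplitude or ellipsoid zone extent, although the data exist.

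**Working it through.** The plan states no figure to reproduce here. The check traces each test from collection to analysis, then counts the observations affected.

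**1. Collection against analysis** (Table 1; Sections 2.2.2, 6.7.4, 6.7.6, 6.7.7, 6.7.8, 9.2.5, 9.2.6)

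| Test | Visits | Eyes | Endpoint | In 9.2.5 list | V2-to-V10 change |
|---|---|---|---|---|---|
| Color and autofluorescence photographs | V1, V9, V10 | both | none | no | no analysis stated |
| ERG | V1, V9 | both | secondary | no | not computable: neither visit exists |
| OCT | V1, V5, V7, V9, V10 | both at V1, V9, V10; study eye at V5, V7 | secondary | no | not computable: no V2 value |
| Dilated ophthalmoscopy | V1, V3, V5, V7, V9, V10 | both | primary safety | yes | summarized descriptively |

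One sentence of Section 6.7.6 gives bilateral OCT at V1 and V10 only. Its last sentence and Table 1 add V9, and that reading is used here.

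Section 9.2.6 also refers to the screening level without a visit number. If that were read as V1, an OCT change from V1 to V10 could be formed. The ERG would still have no V10 value.

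**2. The AE route.** Section 8.1 keeps an abnormal finding out of the AE record unless it comes with signs and symptoms, leads to treatment being stopped, or is clinically relevant in the investigator's view. The collection window is stated in two ways: 30 days after the last dose (Sections 6.5 and 8) and the final visit (Section 8.3; the synopsis also runs to V10). Counting Week 0 as day 0 and using the plus or minus 5-day visit windows:

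- Cohort A: last dose Week 8 = day 56, and 56 + 30 = day 86 (range 81 to 91).
- Cohort B: last dose Week 10 = day 70, and 70 + 30 = day 100 (range 95 to 105).
- V9: day 84 (range 79 to 89). V10: day 112 (range 107 to 117).

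Under the 30-day text, a finding first seen at V10 is always outside the window, since 107 exceeds 105. A V9 finding is inside for Cohort B but can fall outside for Cohort A, since 89 exceeds 81. Under the final-visit text, both are inside.

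**3. Observations affected, 8 subjects.** The first injection is at V2, so V1 is the only pre-dose visit for these three tests.

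- All eyes, baseline included: photographs 8 × 3 visits × 2 eyes = 48 sessions; ERG 8 × 2 × 2 = 32; OCT 8 × (3 × 2 + 2 × 1) = 64.
- Treated eye, post-dose only: photographs 8 × 2 = **16** sessions; ERG 8 × 1 = **8**; OCT 8 × 4 = **32**.

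The second set is the right measure of size, because only a treated eye after dosing can show harm from the drug.

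**The case against.** The strongest reply is that retinal harm does have routes into the primary result. Dilated ophthalmoscopy is a listed safety endpoint, done in both eyes at six visits. The AE query covers observed events, Section 8.1 admits any finding the investigator thinks relevant, and the vision-related note in Section 8.6 is broad. This stands. A reader might infer that evidence of retinal toxicity never reaches the safety result, and the documents do not support that. What remains is that ophthalmoscopy does not measure b-wave amplitude, ellipsoid zone extent or autofluorescence. Otherwise entry depends on case-by-case judgment in an open-label trial, within a window that the protocol states inconsistently.

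A reader might also infer that ERG and OCT are read purely as efficacy, so that a loss counts only as absence of benefit. That goes too far. Section 2.2.2 words both as change, Section 9.2.6 makes change the dependent variable, and Section 9.2.1 specifies two-sided analyses and summaries with minimum and maximum. The one-directional wording is confined to the list in 9.2.6. But a minimum displays a loss only if the change can be computed, and at the stated visits it cannot be.

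The 9.2.5 list is introduced as inclusive, and Sections 9.2.1 and 9.2.8 let a later SAP override the protocol. So one can say only that the documents specify no such analysis, not that none will be done. Settling it now is still better than choosing after open-label data may have been seen.

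Finally, retinal toxicity is an inference. Section 1.1 describes interference with DNA synthesis and repair but says proliferating tissues are generally more sensitive. The methotrexate-specific risks in Section 1.2.1 are keratopathy, hyperemia and injection-site pain. This tempers the urgency. It does not justify leaving collected retinal measures out of a safety result.

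**Conclusion.** The point holds as a gap in specification and should be corrected. Photographs and autofluorescence have no stated use. ERG and OCT have no listed safety summary and, at the visits in Section 9.2.6, no computable change. The treated-eye, post-dose data involved are 16 photograph sessions, 8 ERGs and 32 OCT scans.

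This assumes 8 subjects with complete visits, and that Section 9 is the whole analysis specification available. The totals of 48, 32 and 64 should not be quoted as the size of the problem, because they include baseline and untreated eyes.

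Nor can the fellow eye be relied on to separate harm from the course of disease. The study eye is by design the worse-seeing one, each eye has one pre-dose and one post-dose ERG, and the documents give no repeatability figure. The fellow eye is useful context, not a neutral control.

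**What to change.** In Section 9.2.5, add descriptive safety tables by subject and cohort, without tests:

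- (a) b-wave amplitude change from V1 to V9, losses included, study eye beside fellow eye.
- (b) Central subfield thickness and ellipsoid zone change from V1: study eye at V5, V7, V9 and V10; fellow eye at V9 and V10 only, since it is not scanned at V5 or V7.

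Label the fellow-eye columns as context.

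In Section 9.2.6, replace the words for improvement and increase with change, name OCT, and set V1 as the baseline for ERG and OCT, with V9 as the ERG end point.

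For photographs and autofluorescence, list the investigator's reading at V9 and V10 against V1 only as far as existing site staff can do it. Formal grading would need a reader and a rule that the protocol does not provide.

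The sponsor should also reconcile the two AE collection windows, which decide whether findings first seen at V10 can be recorded.

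The cost is wording in two sections, two tables and one listing, with no new test or visit.

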6.7.9. Corneal Slit Lamp Safety Exam

An undilated slit lamp only exam of the to-be-treated eye will be performed to evaluate the cornea for significant keratopathy prior to intravitreal injection of the IP. Therefore, the Corneal Slit Lamp Safety Exam will be done for subjects in Cohort A at Week 0 (V2) and for Cohort B at Week 0 (V2), Week 2 (V4), Week 6 (V6), Week 10 (V8).

6.8. Investigational Product Intravitreal Injection

Upon completion of the final screening tests at Visit 2, subjects will receive ADX-2191 400 µg/0.05 mL intravitreal injection to the study eye, in accordance with the schedule of events (Table 1). The study eye will be the subject's worse seeing eye. Subjects who are scheduled to receive an intravitreal injection at Weeks 0 (V2), Week 4 (V5), or Week 8 (V7) following completion of testing.

Intravitreal ADX-2191 injections will be performed aseptically after the topical application or subconjunctival injection of an anesthetic agent and 5% povidone iodine to the conjunctiva. Each patient will receive an intravitreal injection of 400 µg/0.05 mL ADX 2191, 3.0 mm posterior to the limbus with a 33-gauge or similar needle.

6.9. Dispense Artificial Tears and Lubricating Ointment

All subjects receiving the investigational product will be prescribed artificial tears and/or lubricating ointment at a minimum of four times daily (QID) throughout the injection phase of the clinical trial. Artificial Tears will be prescribed for Cohort A at Week 0 (V2), Week 4 (V5), and Week 8 (V7) and for Cohort B at Week 0 (V2), Week 2 (V4), Week 4 (V5), Week 6 (V6), Week 8 (V7), and Week 10 (V8).

6.10. Pre-Injection Assessment

Subjects must have a corneal slit lamp exam performed prior to injection of ADX-2191 to assure the safety and viability of the cornea prior proceeding with the investigational treatment. For women of childbearing potential (WOCBP), a urine pregnancy test will be collected and confirmed to be negative prior to undergoing the investigational treatment.

7. CLINICAL TRIAL ACTIVITIES

Clinical trial activities are summarized in the Schedule of Events and Assessments (Table 1).

NOTE: Event weeks are defined as follows: Week 0 is defined as the second and final screening visit.

7.1. Screening Visit A (Visit 1)

- Obtain written informed consent (Section 6.1)
- Review eligibility criteria (Section 6.2)
- Collect demographic information and document medical and social history (Section 6.3)
- Collect samples for urine pregnancy test, if applicable (Section 6.6)
- Perform BCVA (Section 6.7.1)
- Perform LLVA (Section 6.7.2)
- Collect Macular Integrity Assessment (MAIA) (Section 6.7.3)
- Collect Full-field electroretinography (ERG) (Section 6.7.4)
- Collect Dark-Adapted Chromatic Perimetry (Section 6.7.5)
- Collect Macular Optical Coherence Tomography (Section 6.7.6)
- Perform Full Ophthalmic Examination (Section 6.7.7)
- Collect Wide Field Color and Autofluorescence Fundus Photographs (Section 6.7.8)
- Collect concomitant medications (Section 6.4)
- Collect adverse events (Section 6.5)

7.2. Week 0 Screening Visit B (Visit 2)

- Perform BCVA (Section 6.7.1)
- Perform LLVA (Section 6.7.2)
- Collect Macular Integrity Assessment (MAIA) (Section 6.7.3)
- Collect Dark-Adapted Chromatic Perimetry (Section 6.7.5)
- Perform Corneal Slit Lamp Safety Exam (Section 6.7.9)
- Investigational Product Intravitreal Injection (Section 6.8)
- Prescribe artificial tears and/or lubricating ointment (Section 6.9)
- Collect concomitant medications (Section 6.4)
- Collect adverse events (Section 6.5)

7.3. Day 4 (Visit 3)

- Perform BCVA (Section 6.7.1)
- Perform LLVA (Section 6.7.2)
- Perform Full Ophthalmic Examination (Section 6.7.7)

- Collect Dark-Adapted Chromatic Perimetry (Section 6.7.5)
- Collect Macular Integrity Assessment (MAIA) (Section 6.7.3)
- Collect concomitant medications (Section 6.4)
- Collect adverse events (Section 6.5)

7.4. Week 2 (Visit 4)—Cohort B only

- Perform Corneal Slit Lamp Safety Exam (Section 6.7.9)
- Collect samples for urine pregnancy test, if applicable (Section 6.6)
- Investigational Product Intravitreal Injection (Section 6.8)
- Prescribe artificial tears and/or lubricating ointment (Section 6.9)
- Collect concomitant medications (Section 6.4)
- Collect adverse events (Section 6.5)

7.5. Week 4 (Visit 5)

- Perform BCVA (Section 6.7.1)
- Perform LLVA (Section 6.7.2)
- Perform Full Ophthalmic Examination (Section 6.7.7)
- Collect Macular Optical Coherence Tomography (Section 6.7.6)
- Collect Dark-Adapted Chromatic Perimetry (Section 6.7.5)
- Collect Macular Integrity Assessment (MAIA) (Section 6.7.3)
- Collect samples for urine pregnancy test, if applicable (Section 6.6)
- Investigational Product Intravitreal Injection (Section 6.8)
- Prescribe artificial tears and/or lubricating ointment (Section 6.9)
- Collect concomitant medications (Section 6.4)
- Collect adverse events (Section 6.5)

7.6. Week 6 (Visit 6)—Cohort B only

- Perform Corneal Slit Lamp Safety Exam (Section 6.7.9)
- Collect samples for urine pregnancy test, if applicable (Section 6.6)
- Investigational Product Intravitreal Injection (Section 6.8)
- Prescribe artificial tears and/or lubricating ointment (Section 6.9)
- Collect concomitant medications (Section 6.4)
- Collect adverse events (Section 6.5)

7.7. Week 8 (Visit 7)

- Perform BCVA (Section 6.7.1)
- Perform LLVA (Section 6.7.2)
- Perform Full Ophthalmic Examination (Section 6.7.7)
- Collect Macular Optical Coherence Tomography (Section 6.7.6)
- Collect Dark-Adapted Chromatic Perimetry (Section 6.7.5)
- Collect Macular Integrity Assessment (MAIA) (Section 6.7.3)
- Collect samples for urine pregnancy test, if applicable (Section 6.6)
- Investigational Product Intravitreal Injection (Section 6.8)
- Prescribe artificial tears and/or lubricating ointment (Section 6.9)
- Collect concomitant medications (Section 6.4)
- Collect adverse events (Section 6.5)

